During the Covid-19 pandemic elective orthopedic interventions such as THA were often cancelled and the waiting time to surgery increased. Independent of patient characteristics and potential prognostic factors, some surgeries could be performed and other surgeries were cancelled and patients remained on the waiting list, this circumstance allows for a natural experiment. We aimed to perform a target trial emulation (TTE) study on the effect of THA (1). In this study we will compare changes in hip disability in patients with hip osteoarthritis between two groups: THA versus non-surgery (due to the delay in surgery due to the covid pandemic).

We hypothesize that THA is effective compared to non-surgery in reducing hip disability in patients with hip osteoarthritis measured with the Hip disability and Osteoarthritis Outcome Score Physical function Short form (HOOS-PS).

The secondary aim of our study is to assess effectiveness of THA with respect to pain measured with a numerical rating scale (NRS) during weight bearing.

1. INTRODUCTION

Total hip arthroplasty (THA) is one of the most frequently performed orthopedic surgeries. Studies show that THA is an effective treatment to reduce pain and to improve hip function and quality of life in patients with osteoarthritis of the hip. However, the effectiveness of THA has never been investigated by means of a randomized controlled trial (RCT), which is the gold standard to assess effectiveness of an intervention.

During the Covid-19 pandemic, elective orthopedic interventions were defined as not urgent and therefore cancelled. The National Institute for Public Health and the Environment (RIVM) estimated that in 2020 and 2021 in total 32,000 Quality-Adjusted Life Years (QALYs) were not realized due to postponing THA in patients with osteoarthritis of the hip in the Netherlands (9, 10). Better understanding of the treatment effect of THA, compared to non-surgery, could help improve prioritization of interventions.

The ideal research design to investigate effectiveness of THA would be to randomize patients between surgery and (delayed) non-surgery. Such an RCT is deemed unethical due to the effect size of THA shown in observational studies. It is considered unethical to withhold the patients who are allocated to the conservative treatment from the apparent benefits of THA. The required investments in time and money to perform an RCT and expected difficulty to include sufficient patients do not outweigh the benefits of measuring the effect of THA to demonstrate its urgency. Moreover, a potential benefit of research with observational data is, that it better reflects real-world data.

During Covid-19, there were different phases of hospital reduction and restoring of surgical capacity. During periods when surgeries were scaled down nationwide, only emergency surgeries for fractures, infections, and revisions were performed in the orthopedic department. However, our study specifically

focuses on elective primary total hip replacements for osteoarthritis, and during the research period, there was no prioritization based on the severity of symptoms within this osteoarthritis population.

Within the COVID period there were various periods of scaling up and down surgical capacity for elective hip operations, caused by external factors. For example, patient A, scheduled for surgery on Tuesday, proceeded, while patient B, scheduled for Thursday, had to be rescheduled due to changed government or regional policy effective the next day. Patient C had surgery while patient D was cancelled because the surgeon suddenly had to quarantine due to a child or partner with a COVID infection. These issues caused that in some patients THA could be performed and in other patients THA was cancelled.

We assume that whether or not such surgeries took place during the COVID period was beyond the control of patients, doctors and researchers and can be seen as a form of (pseudo)randomization. In a traditional RCT, randomization is done by means of computerized random sequence generation. In an emulation trial (1, 11), randomization is introduced by factors outside of our control, in this case whether THA surgery was cancelled or not due to the COVID-19 pandemic and the resulting scarcity of operating rooms for THA surgery.

An important step in RCT emulation is to verify the validity of the assumption that a comparison between two groups (in our study patients who did and who did not undergo THA surgery within the COVID period) is indeed (pseudo)random and requires analysis. The answer to this question is an outcome of the research, not something we can determine with certainty in advance.

Therefore, the aim of this study is to measure if THA is effective in restoring physical function in patients with osteoarthritis of the hip compared to non-surgery in existing Value-Based Health Care (VBHC) data by means of RCT Target Trial Emulation.

2. RESEARCH QUESTION/ RESEARCH OBJECTIVE

The primary aim of this study is to measure if THA is effective to reduce disability in physical function in patients with osteoarthritis of the hip compared to non-surgery by means of RCT Target Trial Emulation. We hypothesize that THA is effective compared to non-surgery in reducing hip disability in patients with hip osteoarthritis measured with the Hip disability and Osteoarthritis Outcome Score Physical function Short form (HOOS-PS).

Secondary aims of this study are to assess improvement in terms of pain during weight bearing measured on a numerical rating scale (NRS) and assess patient reported improvement in functioning and pain measured by an anchor based question. We hypothesize that THA is effective compared to non-surgery in reducing pain.

3. METHODS

3.1 Study design

Hip osteoarthritis patients eligible for THA and placed on the waiting list for surgery will be included when the preoperative intake questionnaire is completed between 1-4-2020 and 1-1-2022. In a retrospective dataset we compare two standard care strategies: THA and wait-and-see, in which patients did not receive THA and remain on the waiting list. Patients were assigned to one of the two groups based on

whether surgery could be performed or whether THA was cancelled and patients remained on the waiting list. The first group (THA group) consists of patients that received surgery before 1-1-2022 and completed a 3-months postoperative questionnaire before 1-4-2022. The second group (control group) consists of patients which did not receive surgery before 1-1-2022 and completed a waiting list questionnaire before 1-4-2022. The target trial and emulation plan are shown in Figure 1 and the time-schedule of the emulation trial is shown in Figure 2. Patients that received THA on both sides between 1-4-2020 and 1-1-2022 will be excluded. The response rates on follow-up questionnaires will be reported for both groups. We will compare characteristics (age, sex, PROM-outcomes at baseline and physical therapy before the hospital visit) for patients that completed the follow-up questionnaires (completers) and patients that did not complete the follow-up questionnaires (non-completers). In the primary analysis we will correct for patient characteristics.

Target trial → Emulation

[figure not shown]
[figure not shown]

Figure 2: Timeline target trial emulation

THA= Total Hip Arthroplasty

FU = Follow-up

In this study we compare the effect of THA compared to non-surgery on hip disability measured with the HOOS-PS change score from baseline up to approximately 3-months by means of RCT Target Trial Emulation, which aims to mimic a traditional RCT. Function and pain as a secondary outcome are measured by means of patient reported outcome measures (PROMs) pre-operatively and post-operatively or post-waiting list. The pre-operative intake questionnaire and the 3-months postoperative questionnaire are part of standard care. The waiting list questionnaire was administered during the Covid-19 pandemic to monitor patients' health status in two Santeon Hospitals (OLVG and Martini) in all patients who were at least three months on the waiting list. Therefore our study will be performed with data of these two Santeon Hospitals. All data is available through the routinely collected data for hip osteoarthritis within the VBHC program and in addition the outcomes of the administered waiting list questionnaire. Therefore, it is not needed to obtain additional information from patients.

To test the assumption that group allocation is (pseudo)random and cannot be explained by patient characteristics or severity of pain and hip disability at baseline, a logistic regression analysis will be performed on patients within the VBHC data set between 1-4-2020 and 1-1-2022. Group being the dependent variable (THA vs. non-surgery) and age (continuous), sex (M/F), physical therapy before the hospital visit (yes/no), follow-up time in days (continuous), pain at baseline (NRS, continuous) and the HOOS-PS at baseline (continuous) will be included in the model as independent variables. Secondly, we will test the assumption that follow-up time in days is not statistically significantly different between the THA and non-surgery group. Follow-up time is defined by calculating the number of days between the date of the orthopedic visit) and the date of the follow-up questionnaire. Results will be considered statistically significant when $p \leq 0.05$. In case an independent variable has a statistically significant effect on group assignment and/or follow-up time in days is significantly different between the two groups, clinical relevance will be considered and discussed within the research team, for example the effect size on chance to be allocated to the THA or non-surgery group.

We hypothesize that patient characteristics (i.e. sex, age, severity of symptoms at baseline) do not affect group allocation and follow-up time is similar for THA and non-surgery patients. If this is true, the proposed Target Trial Emulation will provide the first evidence on the effectiveness of THA surgery in terms of causal inference.

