1.2 Recruitment and selection of subjects

1.2.1 Screening/selection

Retrospective data will be collected by [name] and the VBHC data analysts at OLVG and Martini hospital.

1.2.2 Study population
 
Patients with hip osteoarthritis that were on the waiting list for THA between 1-4-2020 and 1-1-2022 and had a completed intake questionnaire will be included. The number of patients is dependent on how many patients completed the questionnaires and needs to be investigated. However, based on the waiting list at the time and the number of performed surgeries in the two hospitals, we expect to include at least 100 patients in each cohort (THA group and non-surgery group). Since we use observational data for trial emulation, no sample size calculation is needed (8).

1.2.3 Inclusion criteria
 
Inclusion criteria:
 
 - Patients on the waiting list for primary THA between 1-4-2020 up to 31-3-2022 in OLVG or Martini hospital. - Completed intake questionnaire (HOOS-PS baseline) - Indication osteoarthritis of the hip

1.2.4 Exclusion criteria
 
Exclusion criteria:
 
 - Patients that received THA on both sides within follow-up (1-4-2020 and 1-1-2022) will be excluded. - Patients with other indications than osteoarthritis of the hip were excluded.

1.2.5 Number of subjects/ sample size
 
Since we use observational data for trial emulation no sample size calculation is needed (8). The participants are already exposed to an intervention or not. Differences in the primary and secondary outcomes (PROMs) between groups will be interpreted using 95% confidence intervals and thresholds for clinical relevance which are reported below.

1.3 Data collection: variables and measurement methods
 
1.3.1 Primary outcome measure (dependent variable)
 
Primary outcome is the change score for hip function measured with the HOOS-PS at 3-months postoperative in the THA group and at least 3-months post waiting list in the control group compared to baseline. The HOOS-PS is a 5-item questionnaire that quantifies hip disability. The raw outcome is converted to a Rasch-based interval score ranging from no difficulty (0) to extreme difficulty (100) (3,4,5). The minimal clinically important difference (MCID) for the HOOS-PS is 23 points (6). We will also calculate the minimal important change in our study population, based on an anchor question.

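### Group is set by surgery status on one calendar date, which ties it to intake date, and neither the allocation check nor the outcome models include intake date

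*Combined protocol and SAP*

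**What the plan says.** Section 3.1 Study design takes intakes from 1-4-2020 to 1-1-2022 and defines both groups by one date. "The first group (THA group) consists of patients that received surgery before 1-1-2022", with a postoperative questionnaire before 1-4-2022, defines the first group. The other is defined thus: "The second group (control group) consists of patients which did not receive surgery before 1-1-2022 and completed a waiting list questionnaire before 1-4-2022". The same section says the waiting-list questionnaire was sent out "in all patients who were at least three months on the waiting list", so later surgery did not decide who received it.

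The Introduction describes the contrast as "patients who did and who did not undergo THA surgery within the COVID period" and reports "various periods of scaling up and down surgical capacity for elective hip operations" over that time. It also asserts that "there was no prioritization based on the severity of symptoms within this osteoarthritis population".

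The allocation check (3.1 and 1.4.2 Analyses) is a logistic model of group on age, sex, physical therapy, follow-up days, baseline pain and baseline HOOS-PS, plus a comparison of follow-up days. The outcome models (1.4.2) use the same covariates with group added. The date of the baseline questionnaire is a listed variable in 1.3.2 but is in none of these models. Section 3.1 ends by resting its causal claim on the hypothesis that patient characteristics "do not affect group allocation and follow-up time is similar for THA and non-surgery patients".

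**The concern.** Two things follow from the fixed date.

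- **Control status can depend on what happens after the control outcome.** If a patient completed the waiting-list questionnaire and then had THA before 1-1-2022, that outcome is removed from the controls. The patient counts as THA if the postoperative questionnaire was completed in time, and otherwise is in neither group. For questionnaires completed on or after 1-1-2022, status was already settled.
- **Group is linked to intake date by construction.** Early intakes had much longer to be operated before the cut-off than late ones. By the plan's own account, surgical capacity changed over this period, so calendar time is part of how patients came to be operated or not.

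At stake is the credibility of the pseudo-randomisation check. It looks at baseline characteristics and elapsed time, not at calendar period. Follow-up time is a duration and, in the THA group, includes the wait for surgery, so it cannot stand in for intake date.

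**Working it through.** The plan gives no figure on this point, so there is nothing to reproduce. The steps below are date arithmetic and an illustration.

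**Inputs from the plan.** Intake window and cut-off (3.1); questionnaire after at least three months on the list (3.1), taken as 91 days; group size, where "we expect to include at least 100 patients in each cohort" (1.2.2); relevance threshold of 23 HOOS-PS points (1.3.1, 1.4.2).

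**Assumptions, not in the plan.** Uniform intake; listing and orthopedic visit on the intake day; exponential waits with mean m = 120 to 240 days, unrelated to patient or intake date; full response; postoperative questionnaire 91 days after surgery.

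**1. Dates.** 1-4-2020 to 1-1-2022 is 640 days; 1-10-2021 to 1-1-2022 is 92 days.

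**2. Chance of being operated before the cut-off.** For intake on day t, P(THA) = 1 − exp(−(640 − t)/m).
- t = 0: 1 − exp(−640/120) = 0.995; 1 − exp(−640/240) = 0.93.
- t = 548 (1-10-2021): 1 − exp(−92/120) = 0.54; 1 − exp(−92/240) = 0.32.

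**3. Worked case: one survey round on the cut-off date, m = 120.** Let u = 640 − t.
- Controls have density proportional to exp(−u/120) on 91 to 640. Mean u = 91 + 120 − 549·e^(−4.575)/(1 − e^(−4.575)) = 211 − 5.7 = 205.3 days.
- THA patients have density proportional to 1 − exp(−u/120) on 0 to 640. Mean u = (640²/2 − 120²[1 − 6.333·e^(−5.333)])/(640 − 120[1 − e^(−5.333)]) = (204,800 − 13,960)/520.6 = 366.6 days.
- Control intake is later by 366.6 − 205.3 = 161 days, or 0.44 years.
- Mean follow-up is 205.3 days in controls. In the THA group the mean wait is (76,800 − 14,330 − 13,960)/520.6 = 93.2 days, so follow-up is 93.2 + 91 = 184.2 days. The difference is 21 days.

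Follow-up times are thus close while intake dates lie about five months apart.

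**4. Other survey timings (simulation; m = 120 / 180 / 240).**

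| Survey | Control intake later by (years) | Waiting-list outcomes lost per control kept |
|---|---|---|
| Each patient at day 91 | 0.63 / 0.56 / 0.51 | 2.05 / 1.44 / 1.09 |
| One round, day 610 | 0.36 / 0.30 / 0.26 | 0.28 / 0.18 / 0.13 |
| One round, day 640 | 0.44 / 0.37 / 0.33 | 0 / 0 / 0 |

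**5. The allocation check at 100 per group, baseline variables unrelated to group.** With one round at day 610 or 640, the follow-up-time test was non-significant in 38–70% of runs and every planned test in 28–55%. Intake date, when tested, was significant in at least 99%. With day-91 surveys the follow-up-time test was significant in every run, so the check flags a difference, but in elapsed time and not in period.

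**6. Possible effect on the estimate.**
- *Calendar drift.* Each assumed 1 point per year of drift in HOOS-PS change by intake date moves the THA coefficient by 0.3–0.5 points with follow-up time in the model.
- *Selection.* This is 0 if surgery timing is unrelated to the waiting-list course. Suppose instead that 1 SD of worsening (assumed 15 points) raised the surgery rate by 22–49%, with mean waits of 60–240 days. With day-91 surveys and an effect acting only after the survey, THA is understated by 1.2–3.1 points, and by 0 once pre-surgery questionnaires are counted as control outcomes. If the effect acts from listing, the figures are 2.6–10.1 as planned and 1.1–7.9 after that recoding. With one round on the cut-off date they are 3.2–12.7 and recoding changes nothing.

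**The case against.** The strongest reply is that no bias is shown. Survey dates and waiting times are not given, and the two figures with the emulation plan and timeline are not reproduced in the copy reviewed. Drift is undocumented and, at the assumed rate, tiny beside 23 points. The Introduction denies prioritisation by severity; if surgery timing is indeed unrelated to the waiting-list course, selection is nil. All of this stands. The planned check cannot test that last condition, because it uses only baseline variables and follow-up time.

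A reader might infer from the larger selection figures that the fixed date could distort the effect by 10 points or more. The documents do not support this. Those figures need worsening to drive surgery from listing, and most of the bias remains, or all of it with a round on the cut-off date, when the controls are recoded. It comes mainly from informative surgery timing and not from the cut-off rule.

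The rule also matches the contrast stated in the Introduction, and the plan treats pseudo-randomness as something to be examined. With day-91 surveys the planned check would flag follow-up time and prompt discussion in the team. That is fair, but 3.1 and 1.3.2 leave the survey timing open, and with a single round the check can pass.

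A reader might also infer that intake date belongs in the primary outcome models. This does not follow. Intake date strongly drives allocation and has no documented effect on outcome, so adjusting for it can amplify residual selection. Where worsening speeds surgery from listing, two separate simulations found that adding it increased the bias, by 0.1–1.0 points in one and about 0.2–2.2 in the other. That is comparable to or larger than the drift it would remove.

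**Conclusion.** The concern holds as a gap in the allocation check and in the condition attached to the causal claim. The fixed-date rule, the exclusion of waiting-list outcomes followed by THA before the cut-off, the link between group and intake date, and the absence of intake date from every model all follow from the text. The link is a strong dependence and not full determination, and it arises even with purely random waits. The missing timeline figures could clarify the survey dates but would not alter the written group definitions or covariate lists.

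The size and direction of any bias in the THA effect cannot be derived from the documents. It is zero if outcomes do not drift with calendar time and surgery timing is unrelated to the waiting-list course. Under modest departures it is small against 23 points. Nothing here shows that the sign or clinical relevance of the result would change. The intake gaps and pass rates rest on the assumed waits, uniform intake and survey timing. This is worth fixing before analysis, with medium confidence.

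**What to change.** 1. Keep the grouping in 3.1 and the planned primary outcome models.
2. Add intake date (date of the baseline questionnaire) or calendar period to the allocation check, with one row per patient under the planned grouping. Show its distribution by group, and make the causal wording at the end of 3.1 conditional on this result as well.
3. As sensitivity analyses only: (a) add intake date to both outcome models, with and without follow-up time; (b) count every waiting-list questionnaire completed before any THA as a control outcome, with standard errors clustered by patient.
4. Report the survey dates and the number of patients with a questionnaire followed by THA before 1-1-2022.

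No new data are needed. The downsides to state in the SAP are:
- The interval widens in the intake-date models that keep follow-up time. Under the assumptions above (mean waits 120–240 days), the THA standard error rises by 4–13% with day-91 surveys and 16–28% with a single round. Without follow-up time the single-round rise is 4–16%.
- With a single round, intake date and follow-up time are nearly collinear among controls.
- Adjusting for intake date may amplify residual selection bias.
- Recoding neither removes selection that acts from listing nor aligns time zero, and with a single round it leaves the calendar gap unchanged.

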
3.5.2. Secondary outcome measure
 
Secondary outcomes are change scores on other patient reported outcome measures (PROMs). Pain during weight bearing is measured on a numerical rating scale (NRS) ranging from 0-10. The minimal clinically important difference (MCID) for the NRS is 2 points. The anchor based questions range from 1-7 for functioning and pain. These PROMs were obtained at baseline (except the anchor based question) and at 3-months postoperatively and at least 3-months post waiting list

1.3.2 Overview of variables and measurement instruments

Variable	Measuring instrument/ Source of data	Outcome values	Measurement time
Sex	VBHC data (source is EHR*)	numeric (1 = F, 2 = M) 999 or NA is missing	Baseline
Age at time of inclusion	VBHC data (source is EHR*)	Numeric 999 or NA is missing	Baseline
Date for order THA	VBHC data (source is EHR*)	date (YYYY-MM-DD)	Baseline
Surgery date	VBHC data (source is EHR*)	date (YYYY-MM-DD) or not applicable (NA)	Date of surgery
Date completion of baseline questionnaire	VBHC data (source is EHR*)	date (YYYY-MM-DD)	Baseline
HOOS_PS_BL	HOOS_PS_PI VBHC data (source is EHR*)	HOOS-PS personal interval level score at baseline. Numeric (0-100) 999 or NA is missing	Baseline
Pain weight bearing at baseline	NRS VBHC data (source is EHR*)	numeric (0-10) 999 or NA is missing	Baseline
Patient followed physical therapy before hospital visit	VBHC data (source is EHR*)	No (0) / Yes (1) 999 or NA is missing	Baseline
Date completion of 3-months postoperative questionnaire	VBHC data (source is EHR*)	date (YYYY-MM-DD) or not applicable (NA)	3-months PO
Date completion of 3-months waiting list questionnaire	VBHC data (source is EHR*)	date (YYYY-MM-DD) or not applicable (NA)	≥ 3-months waiting list
HOOS_PS_3M_PO	HOOS_PS_PI VBHC data (source is EHR*)	HOOS-PS personal interval level score at 3-months postoperatively. Numeric (0-100) 999 or NA is missing	3-months PO
HOOS_PS_3M_WL	HOOS_PS_PI Waiting list questionnaire (source is EHR*)	HOOS-PS personal interval level score at 3-months waiting list. Numeric (0-100) 999 or NA is missing	≥ 3-months waiting list

Pain weight bearing at 3-months postoperatively	NRS VBHC data (source is EHR*)	numeric (0-10) 999 or NA is missing	3-months PO
Pain weight bearing at 3-months waiting list	NRS VBHC data (source is EHR*)	numeric (0-10) 999 or NA is missing	≥ 3-months waiting list

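### Pandemic cancellation or lost capacity is the stated basis of assignment, but no group rule, eligibility criterion or variable carries it, so some controls may be waiting for their own or medical reasons

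*Combined protocol and SAP*

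**What the plan says.** All references are to the combined protocol and SAP.

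- **Rationale (1. Introduction).** The source of randomisation is "in this case whether THA surgery was cancelled or not due to the COVID-19 pandemic and the resulting scarcity of operating rooms for THA surgery".
- **Assignment in words (3.1 Study design).** Patients were assigned on "whether surgery could be performed or whether THA was cancelled and patients remained on the waiting list".
- **Assignment as rules (3.1).** "The first group (THA group) consists of patients that received surgery before 1-1-2022 and completed a 3-months postoperative questionnaire before 1-4-2022". For the comparator: "The second group (control group) consists of patients which did not receive surgery before 1-1-2022 and completed a waiting list questionnaire before 1-4-2022".
- **Waiting-list form (3.1).** It was given in two hospitals "in all patients who were at least three months on the waiting list".
- **Eligibility (1.2.3 and 1.2.4).** Patients must be on the waiting list, have a completed intake questionnaire and have hip osteoarthritis. Those with THA on both sides are excluded.
- **Variables (1.3.2).** For scheduling, the table lists "Date for order THA" and the date of surgery performed. The other dates are those of the questionnaires.
- **Check and adjustment (3.1 and 1.4.2).** The logistic model for group and the outcome regressions use the same covariates: age, sex, prior physical therapy, follow-up days, baseline pain and baseline HOOS-PS.
- **Causal reading (last paragraph of 3.1).** It is conditional on patient characteristics not affecting allocation and on similar follow-up time.

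**The concern.** The pandemic disruption is what separates this study from an ordinary comparison of operated and still-waiting patients. The plan names it as the basis of assignment but does not turn it into a rule or a data field. A patient who put off surgery, or was deferred as medically unfit, and who stayed listed and returned the form is counted in the same way as a patient whose slot was lost to the pandemic.

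Such deferrals may be related to prognosis. To that extent they bring back the confounding that the natural experiment is meant to remove. Balance on the measured covariates could then be taken as support for the causal reading although part of the control group was never subject to the pseudo-randomising mechanism.

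**Working it through.** The plan gives no figure to reproduce on this point. The check has three steps.

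**1. Does cancellation status change anyone's group?** The dated rules of section 3.1 were applied to hypothetical patients, using the listing date as the intake date. Each patient was classified once with the cancellation status shown and once with it reversed.

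| Hypothetical patient | Group | Status reversed |
|---|---|---|
| Listed Sept 2020, cancelled Dec 2020, operated June 2021, postoperative form Sept 2021 | THA | THA |
| Listed Sept 2020, not cancelled, operated Dec 2020, postoperative form March 2021 | THA | THA |
| Listed May 2021, cancelled, still waiting, waiting-list form Sept 2021 | Control | Control |
| Listed May 2021, deferred by choice or for medical reasons, waiting-list form Sept 2021 | Control | Control |
| Listed 1 Dec 2021, never cancelled, waiting-list form 5 March 2022 | Control | Control |
| Listed May 2021, left the list before any waiting-list form | Neither | Neither |

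Cancellation status changes no patient's group. The third and fourth patients cannot be told apart with the listed variables.

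**2. Could the planned check reveal the difference?** Only in part. If deferral depends on symptoms, baseline pain and HOOS-PS will show some of it in the logistic model and remove some of it in the outcome regression. Comorbidity, fitness for surgery and reason for deferral are not in the variable table. Deferral that depends on these, and not on the measured covariates, leaves the check clean.

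**3. How large could the bias be?** Let q be the share of controls deferred by choice or for medical reasons. Let d be the difference between their mean HOOS-PS change and that of capacity-delayed controls. Then

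control mean = (1 − q) × m + q × (m + d) = m + q × d,

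where m is the mean for capacity-delayed controls. The bias in the control mean is q × d. The documents give neither quantity, so both ranges are assumptions:

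- q = 0.10, d = 5: 0.10 × 5 = 0.5 points
- q = 0.10, d = 15: 0.10 × 15 = 1.5 points
- q = 0.30, d = 5: 0.30 × 5 = 1.5 points
- q = 0.30, d = 15: 0.30 × 15 = 4.5 points

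The sign of d is unknown, so the bias can go either way. Against the plan's MCID of 23 points (1.3.1 and 1.4.2), the range is 0.5/23 = 2% to 4.5/23 = 20% (19.6% before rounding). The calculation takes the THA mean as unaffected and d as what remains after covariate adjustment.

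**The case against.** The strongest defence is that section 3.1 does name cancellation as the basis of assignment, that the Introduction states there was no prioritisation by symptom severity, and that baseline pain and function are both tested and adjusted for. The causal statement is conditional, and the Introduction treats the validity of the assumption as something the study will find out. All of this stands. It limits the point to a stated basis that is not made operational. It does not supply the reason why a control was not operated. The statement on prioritisation does not address deferral by the patient or for medical reasons.

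A reader might infer more than the documents support:

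- **That controls may be unoperated for any reason whatever.** They must still be listed, have been listed for at least three months and have returned the form. The documents do not say whether patients who deferred by choice or for medical reasons stayed on the list; the concern applies to those who did.
- **That patients never given a date contaminate the control group.** The Introduction includes scarcity of operating rooms in the mechanism. Patients without a date for that reason belong in the comparison.
- **That rescheduled patients are misclassified.** The plan's example, "patient B, scheduled for Thursday, had to be rescheduled due to changed government or regional policy effective the next day", falls in the THA group if operated before 1-1-2022. That is consistent with section 3.1, which describes controls as having remained on the list, and an external cancellation followed by surgery does not by itself create confounding by indication.
- **That the allocation check is blind to the problem.** It is partly sensitive, through baseline symptoms.

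Figure 1, which sets out the target trial and its emulation, is not shown in the text available and may say more about assignment. The variable table would still lack a field to apply such a rule.

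**Conclusion.** The point holds in this limited form: the stated basis of assignment is missing from the operational group definitions, the eligibility criteria and the variable list. Following the plan as written can admit controls whose wait had nothing to do with capacity, and a clean allocation check would not exclude this.

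The size is unknown. Under the assumed shares and differences it is at most 4.5 HOOS-PS points. A bias of that size could alter the verdict on clinical relevance only if the estimated difference lay between about 18.5 and 27.5 points (23 ± 4.5). The documents do not support the inference that the problem would overturn a large effect or invalidate the study. What it affects is the strength of the causal claim. It should be fixed, but the study does not stand or fall by it.

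**What to change.** 1. **Before extraction**, add planned surgery date(s), any cancellation or deferral, and its reason (capacity, policy or staff; patient choice; medical), where hospital planning records hold them. Timing matters: section 2.2 says the data are used anonymously and section 3.2.3 gives the key as not applicable, so adding reasons later may not be possible.
2. **Sensitivity analysis.** Repeat the primary analysis without patients deferred by choice or for medical reasons, excluding them from both groups. Removing them from the controls alone would leave similar patients in the THA group and could itself create imbalance. Keep patients who had no date because capacity was scarce.
3. **If reasons cannot be retrieved**, describe the comparator throughout as *remaining on the waiting list for at least three months, reason not recorded*. Amend the last paragraph of section 3.1 so that the causal claim does not follow merely from balance on the measured characteristics and follow-up time.

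The cost is a few retrospective fields, one protocol paragraph and one further analysis. Some reasons will be missing, and the sensitivity analysis will have a somewhat smaller sample. The documents do not mention planning records, so retrieval is not assured. The fallback is a change of wording only.
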